i. All Participants: Coping Plan, follow-up check-ins, and COVID-19 messages est. *N* = 137 All study participants will receive a one-hour support visit (either by phone or in-person) from a study staff person to develop an individualized plan for coping with life's challenges. This modified safety plan will include information on who and where they can get help during tough times or when they are feeling down. It will also include some ways they can work through these challenges. The plan is an adapted version of the evidence-based Safety Planning Intervention (described in background section) and was designed to address the underlying risk of suicide and other mental health stress as well. A couple of days after this visit, a study staff person will call the participant to check-in on how things are going and make additional community referrals. A second check-in will occur the following week. All staff will receive additional training on completing a coping plan. Finally, all study participants will receive up to 3 COVID-19 safety messages. Participants may choose to receive caring messages by text message or paper postcard sent in the mail. Participants with text messages that bounce back to the Johns Hopkins team at any point during the study will be automatically switched to receiving postcard messages until an updated phone number is provided.

ii. Intervention Group ONLY: Caring Contacts est. N = 69

The intervention group will also receive up to 7 culturally responsive caring messages from the research team over a period of three months.

iii. Assessments

During the screening/baseline assessment and all subsequent assessments (30 days $[\pm 10]$, and 90 days $[\pm 10]$ after screening/baseline) all study participants will be contacted to participate in a self-administered survey via REDCap. Paper copies of the questionnaire, along with a scoring manual for study staff to use at baseline for symptom screening), will be available as back-up. This survey will include the mental health measures described below, as well as questions regarding the participants' attitudes and beliefs about COVID-19 prevention strategies (e.g., masking when appropriate, visiting a health care provider), testing, and vaccination. The domains and survey items for

parents/caregivers are listed in Table 5 and the domains and survey items for youth are listed in Table 6 below.

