A username and password are required to access the REDCap system. Study staff will launch the assessments on a tablet or, if preferred, via a link to the survey that participants can access from their phone or personal computer/tablet. If needed forms can be printed and provided on paper, but data must be entered into REDCap as soon as the staff member has it back at the office. Tablets will be synced daily with REDCap using a secure Wi-Fi connection available at the study site. For the assessments completed via phone, staff will read the questions to the participant. Study staff are trained to provide additional information to clarify questions as necessary. If in-person, the study staff member will provide the tablet to the participant so that they can complete the assessment via selfreport. If done on paper, the study staff will provide the paper packet. They will be available if questions should arise. Data collected through REDCap is automatically stored on a Johns Hopkins HIPAA compliant, secure server. Direct data entry into REDCap eliminates the need for separate data entry and coding. Any data that is collected via hard copy will be entered into REDCap. Once entered into REDCap, for any participant who scores above pre-established cutoffs on mental health instruments or indicates suicide risk (see Safety Monitoring section), a notification will appear on the tablet to the interviewer to proceed with safety procedures. An additional email alert to the site supervisor, PI and study coordinator will also occur when the data is uploaded to the server to promote communication and allow for timely follow-up. Data will be downloaded from REDCap as a complete database into de-identified Excel and Stata files that will be stored on Johns Hopkins' HIPAA compliant, secure server. Data will be retained until the end of study analysis or three years after the final participants exit the program, whichever comes first.

Each assessment timepoint include the following scales or items by type of respondent:

Table 5. Parent/Caregiver Time points and Measures

Domain	Instrument	Items	Baseline/ Screener	30 Days	90 Days	Included in PSS secondary data analysis
Adult Self-Report						
	Menta	l Health	Outcome Don	nains		
General Distress	Kessler	11	Χ	Χ	X	X
Depression Symptoms	CESDR-10	10	X	Х	X	X
Anxiety Symptoms	PROMIS	8	Х	Х	Х	X
	Intermediary Ou	ıtcome [Domains/Prog	ram Fee	dback	

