Center for Epidemiologic Studies Depression Scale Revised (CESDR-10) (Youth Self-Report): The CESDR-10 is a revised 10 item self-report questionnaire which measures depressive symptoms in adult general populations. It utilizes a 0-30 scale, in which a score of 8+ is considered high risk. The CESDR-10 also has one item that ask about recent suicide ideation.²²

Screen for Child Anxiety Related Emotional Disorders (SCARED) (Parent-Report and Youth Self-Report): The youth self-report SCARED survey can be used with those aged 8-18 years. It includes 41 items and five scales which measure somatic/panic, general anxiety, separation anxiety, social phobia, and school phobia. SCARED uses a 0-82 scale where a score of 25+ is high risk.²⁵

Youth Resilience: Two items related to social connections from the Child/Youth Resilience Scale were selected to assess youth resilience.²⁰

2. Describe the number and type of study visits and/or contacts between the study team and the participant, how long they will last, and where/how they will take place.

The number and type of study visits are described in Table 7 below.

Table 7. Number and type of study contacts by intervention component and study arm

Study Arm	Activity	Number of Contacts	Estimated Length of Time	Where/How
Coping plans only (Comparison Group)	Coping plan	1	1 hour	In person, over the phone
	Check-in calls/visits	2	15-30 minutes each (total time: 30 minutes- 1 hour)	In person, over the phone
	REDCap Survey	3	15-30 minutes (total time: 45 minutes-1.5 hours)	In person, over the phone, email, text
	COVID Prevention Messages	3	N/A	Text message, ground mail

IRB #00020570 +CiM/HSP research plan v7 14Nov2022

Pls: [name] (Faculty PI) & [name] (Navajo Community PI)

Caring contacts group (Intervention group)	Coping Plan	1	1 hour	In person, over the phone
	Check-in calls/visits	2	15-30 minutes each (total time: 30 minutes- 1 hour)	In person, over the phone
	Caring Contacts	7	N/A	Text message, ground mail
	REDCap Survey	3	15-30 minutes (total time: 45 minutes-1.5 hours)	In person, over the phone, email
	COVID Prevention Messages	3	N/A	Text message, ground mail

3. Describe the expected duration of the study from the perspective of the individual participant and duration overall.

Caregivers and youth will be enrolled in this study for three months.

4. Provide a brief data analysis plan and a description of variables to be derived.

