C. If genetic/genomic analyses are planned, address whether the data will be contributed to a GWAS or another large dataset. Address returning unanticipated incidental genetic findings to study participants.

N/A

D. If clinical or laboratory work will be performed at JHU/JHH, provide the JH Biosafety Registration Number.

N/A

E. If you will perform investigational or standard diagnostic laboratory tests using human samples or data, clarify whether the tests are validated and/or the lab is certified (for example is CLIA certified in the U.S.). For clinical tests of human biospecimens, no results may be returned unless completed in a certified lab. Explain the failure rate and under what circumstances you will repeat a test. For all human testing (biomedical, psychological, educational, etc.), clarify your plans for reporting test results to participants and/or to their families or clinicians. Address returning unanticipated incidental findings to study participants.

N/A

- F. If your study involves medical, pharmaceutical, or other therapeutic intervention, provide the following information:
 - a. Will the study staff be blind to participant intervention status?

No blinding will occur.

b. Will participants receive standard care or have current therapy stopped?

Yes, participants will be able to access the current standard of care; participants will be able to access all medical, mental, or behavioral health services they desire. During any study visit, research staff can direct individuals to appropriate sources of information as needed.

c. Will you use a placebo or non-treatment group, and is that justifiable?

The comparison group will receive an evidence-based tool (coping plan + two additional check-in calls or visits) and information on community support services (e.g., tribal behavioral health).

d. Explain when you may remove a participant from the study.

We will not remove any participants from the study.

e. What happens to participants on a study in which there is a medical intervention when the study ends? Will participants continue to have access to the study intervention? What happens if they leave the study early?

N/A

f. Describe the process for referring participants to care outside the study, if needed.

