	Other Approved Platforms: □ JH One Drive/JHSPH OneDrive □ JH IT-Managed Network Storage □ JHM/JHSPH Qualtrics □ JHSPH HPCC □ JHSPH SharePoint □ JHSPH Shares □ JHU REDCap □ MARCC-Secure Environment
	X Platform(s) not managed by JH/JHSPH, not pre-approved, and require a risk assessment review from JHSPH Data Security (please describe): We will need to upload first name and phone numbers of enrolled and randomized participants into Textlt directly to allow for MMS. The Twilio/REDcap integration does not allow sending of MMS which is integral to the intervention. Thus, Twillio is being phased out as we switch to Textlt due to inability of Twilio to send MMS.
	 Describe risk mitigation measures that are in place: TextIt is a cloud-based service to generate texting campaigns and chatbots. TextIt hosts with Amazon Web Services, and all data is stored solely in the United States. TextIt servers are protected by firewalls, and all access to those servers is permitted only through encrypted channels that are FIPS-140-2 compliant.
	Our TextIt subscription is password-protected and requires two-factor authentication. Only study management team members have access to the username and password that is associated with the account. This information is kept on password-protected computers and not saved anywhere else.
	 Note: The following are examples of platforms/storage solutions that are not pre-approved to store identifiable information and require a risk assessment from JHSPH Data Security: Other solutions not managed by IT@JH, e.g., commercial cloud storage (Box, Dropbox, iCloud, personal OneDrive, Google Drive, Amazon storage, etc.)
	JHU Independent Departmental Servers
	Local Computer owned by JH
	 Other computers or devices owned/managed by study team members and used for other than secure web access
	USB/Portable data storage device

10. Access to Data and Access Controls: How will you ensure that only authorized individuals can
access the data? What access controls will you put into place to ensure that only authorized
individuals may access and use the data. (For example, OneDrive guidance illustrates how to share
files with "people you specify". JHSPH-Shares addresses providing permissions to individual people.)
Check all that apply. Note: If you need assistance implementing secure access controls, contact
[contact].
 Will provide access to data in accordance with OneDrive/JHSPH-Shares guidance posted on JHU IT websites

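### The plan rules out all blinding, yet staff may read and clarify self-reported symptom items by phone; survey staff could probably be masked to allocation at little cost

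*Combined protocol and SAP*

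**What the plan says.** Section V.C.5.F, item a, asks "Will the study staff be blind to participant intervention status". The answer is "No blinding will occur". No reason is given, and no exception is made for those who administer outcome surveys.

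Section V.C.1.iii (Assessments) makes self-completion the default: "all study participants will be contacted to participate in a self-administered survey via REDCap". The same section then allows for interviewer involvement: "For the assessments completed via phone, staff will read the questions to the participant", and "Study staff are trained to provide additional information to clarify questions as necessary". The share of surveys done by phone is not given.

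Sections I and V.C.1 and Tables 4 and 7 give both arms the same coping plan, two check-ins and COVID-19 messages. The intervention arm adds up to 7 caring messages, by text or postcard.

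On the texting platform, section VI item 8 says "Only study management team members have access to the username and password". Section V.C.1.i speaks of "text messages that bounce back to the Johns Hopkins team". Neither passage says who mails the postcards.

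Under section V.C.5.A a study team member triggers randomisation inside the participant's REDCap form. Section XI.A.3 sets the main Aim 1 time point at Wave 3 of Project SafeSchools.

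**The concern.** Aim 1 compares self-reported depression and anxiety between arms. Such scores can move with the tone, prompting or explanation of the person reading the items. Section V.A.1 adds that most staff already have a relationship with potential participants. A reader who knows the arm can therefore introduce a difference between arms, in either direction, that the caring messages did not cause.

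In many behavioural trials this is unavoidable, because the person delivering the treatment must know the arm. Here the staff-delivered components are the same in both arms, so the exposure looks avoidable. The pilot is meant to inform a fully powered study (section III.A), so a bias left in now could carry forward into its planning.

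**Working it through.** **1. The plan's own figure.** Inputs from section III.B: 75 adults analysed, equal allocation, alpha 0.05, power 0.80, d = 0.66, SD 6.4 (CESDR-10) and 5.3 (PROMIS). Sidedness is not stated; two-sided reproduces the figure.
- Two-sample t-test, 37 per arm: detectable d = 0.660. At 37.5 per arm: 0.656.
- 0.66 × 6.4 = 4.22 and 0.66 × 5.3 = 3.50, matching Table 1 (4.2 and 3.5).

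The figure reproduces. Masking survey staff changes none of these numbers.

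**2. What the documents establish about feasibility.**

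| Step | Stated | Not stated |
|---|---|---|
| Coping plan, check-ins, COVID-19 messages | Same in both arms | – |
| Caring texts | Sent from an account held by study management | – |
| Caring postcards | Offered as an alternative to text | Who mails them |
| Randomisation | A study team member selects it in REDCap | Whether that person also gives surveys, and who sees the result |
| Later field-staff tasks | None described that depends on arm | – |

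So central control of texts is documented. Central mailing of postcards, and the absence of any need for field staff to know the arm, are inferences.

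**3. Illustrative size.** The documents give no figure for interviewer bias. Assume that arm-aware reading shifts scores by b SD, differentially between arms, in the share p of surveys that are staff-read. The spurious arm difference is then p × b SD. With 37 and 38 per arm, the standard error is √(1/37 + 1/38) = 0.231 SD, with 73 degrees of freedom. The two-sided rejection rate with no true effect follows from the noncentral t with noncentrality p × b / 0.231.

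| p (assumed) | b (assumed) | p × b (SD) | CESDR-10 points (× 6.4) | Share of 4.2 points | False-positive rate |
|---|---|---|---|---|---|
| 25% | 0.1 | 0.025 | 0.16 | 4% | 5.1% |
| 25% | 0.2 | 0.05 | 0.32 | 8% | 5.5% |
| 50% | 0.1 | 0.05 | 0.32 | 8% | 5.5% |
| 50% | 0.2 | 0.10 | 0.64 | 15% | 7.1% |
| 100% | 0.1 | 0.10 | 0.64 | 15% | 7.1% |
| 100% | 0.2 | 0.20 | 1.28 | 30% | 13.7% |

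The range of about 7% to 14% needs every survey to be staff-read. With a quarter to a half staff-read, the same shift gives about 5.1% to 7.1%.

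**4. Time point.** Section XI.A.3 places the main Aim 1 comparison at Wave 3. How Wave 3 surveys are administered is not described in these documents. Section V.A.1 says study staff already work on the parent cohort, so the same people may collect Wave 3.

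**The case against.** The strongest reply is that most surveys may involve no interviewer. Self-completion is the default. In person, the participant is handed the tablet, and links and paper packets are also offered. This stands, and it is why the size has to be scaled by an unknown phone share.

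Second, participants know whether they receive caring messages, and they rate themselves. Masking staff leaves that expectancy untouched. This also stands: the change removes one source of bias, not the main one that an open-label, self-reported design carries.

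Third, this is a pilot whose stated main objectives concern materials and procedures. That lowers the stakes, but Aim 1 still claims to determine effectiveness.

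Three stronger readings are tempting, and the documents do not support them:
- A reader might infer that all messages are sent centrally and that field staff demonstrably need no allocation. The account restriction covers texts only. The reference to bounced texts does not settle who is central, since section VII.D lists a Johns Hopkins office among the visit venues.
- A reader might take Table 7 to mean that survey mode differs by arm, because the comparison cell reads "In person, over the phone, email, text" and the intervention cell omits text. Section V.C.1.iii and section VII.D describe survey access without regard to arm, and VII.D ties it to participant preference. A clerical omission is the likelier explanation.
- A reader might infer that the 90-day feedback items unmask the interviewer before the symptom scales are given. Tables 5 and 6 list them last, and the order of administration is not stated.

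**Conclusion.** The point holds as an inexpensive improvement, not as a flaw that invalidates the trial. A blanket refusal of blinding, combined with staff reading and clarifying subjective items, exposes phone-collected outcomes to interviewer bias, and nothing in the documents explains why survey staff could not be masked.

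The size is illustrative. It rests on an assumed 0.1 to 0.2 SD shift and an assumed staff-read share. The upper figures should not be quoted without the condition that all surveys are staff-read. Feasibility rests on the inference that postcards can be handled by study management and that field staff have no unstated arm-dependent task; the sponsor should confirm both.

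**What to change.** Replace the blanket answer in section V.C.5.F, item a, with a statement that staff who administer follow-up surveys are masked to allocation, and that participants and the study management team are not. To support it:

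- A study management team member performs the REDCap randomisation (section V.C.5.A) and sends both texts and postcards (section V.C.1).
- REDCap user rights hide the allocation field from survey staff.
- Masking covers the 30- and 90-day surveys and, where the same staff collect it, Project SafeSchools Wave 3.
- The symptom scales are given before the 90-day feedback items.
- Survey mode and any unmasking are recorded for each assessment.

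Separately, as a minor wording correction, list the same survey modes for both arms in Table 7.

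The cost is a change of user rights, some wording and two recorded fields. Sample size and detectable effect are unchanged. The documents show no need for extra staff, but the management team takes over the randomisation click and, if it does not already do so, the postcards. Participants may still reveal their arm, and their own expectancy remains.

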- 5. Suicide Risk Plan. An imminent risk procedure was developed by JHU for previous studies to ensure triage and access to emergency care for suicidal individuals. Risk will be gauged by immediately scoring the suicide-related questions. Questions from the CESDR-10 that indicate recent suicide ideation (i.e., in the last two weeks) for adults and youth will be identified and flagged in REDCap and an automatic alert setting for these questions will automatically alert senior members of the study team. Study team members have all received Applied Suicide Intervention Skills Training (ASIST) and can respond in crisis situations. If the study team receives an alert for suicidal ideation based on a participant completing the survey instruments online (adults only; youth are not allowed to complete surveys online) after working hours, a text will be sent to them that contains the National Suicide Prevention hotline number and crisis text line. Study staff will follow up with them within 24 hours to provide additional support and resources. To make it possible to send the text message, we will enable Twilio integration in REDcap. See the 'Miscellaneous Documents' for the details of this Suicide Risk Safety Procedures.
- 6. **Staff training and familiarity with local context.** We have attempted to minimize these risks by employing Native paraprofessionals who are trained in active listening, problem-solving, maintaining confidentiality, assessing worsening of symptoms, providing support, and other relevant procedures, including basic relaxation techniques to ensure each participant's comfort and well-being. If any participant becomes distressed during the surveys or interviews, a break will be provided, or the survey/interview will be stopped, and the research staff will work with the participant to reduce the participant's distress using basic relaxation techniques. If the participant's distress is not able to be addressed by these approaches, the Research Program Assistants will ask if the participant wishes to address the distress in another manner and will facilitate the participant's request when possible. In addition, Research staff can enlist the site supervisors at each site to talk with the participant via phone and facilitate referrals if necessary.
- 7. **Data Storage and Protection.** No unique identifiers will be collected in data collection forms or handwritten notes

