- 8. Adverse Event Monitoring. Study staff, a supervisor, or community mental health specialists on staff will assist participants in obtaining additional services for adverse events. The PI will recommend premature study termination based on defined safety procedures.
- C. Describe the anticipated frequency and severity of the harms associated with the risks identified above; for example, if you are performing "x" test/assessment, or dispensing "y" drug, how often do you expect an "anticipated" adverse reaction to occur in a study participant, and how severe do you expect that reaction to be?
 - In general, we do not expect any adverse reaction to the study activities.
- D. Describe the research burden for participants, including time, inconvenience, invasion of privacy in the home, out of pocket costs, etc.

IRB #00020570 +CiM/HSP research plan v7 14Nov2022

PIs: [name] (Faculty PI) & [name] (Navajo Community PI)

Participant burden is described as follows: Study activities will be provided via an in-person visit, phone calls, text messages and/or mailed postcards. In person visits will take place either at school, at the Johns Hopkins office, in a private space in the community, or at the person's home. Youth/caregiver participants will have up to two study visits (one for consent and coping skills planning) each lasting approximately 1 hour and two follow-up phone calls or in-person check-ins each lasting around 30 minutes for a total active study time of 3 hours.

Assessments will be done either virtually (via phone, Zoom, or REDCap survey sent directly to a participant's smart phone), in-person at a safe distance and while following COVID-19 safety protocols depending on the participant's preference, or by a self-administered paper packet dropped off by a study team member. There are 3 assessments for each participant type, which should take 15-30 minutes each to complete. Thus, total time anticipated for data collection is a maximum of 1.5 hours.

All study participants are expected to spend a maximum of 4.5 hours total participating in this research study. For participants who are not eligible to continue their participation after symptom screening, their maximum total time spent participating in the study should not exceed 1.5 hours (consent visit and baseline screening).

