E. Describe how participant privacy, and if relevant – family privacy - will be protected during data collection if sensitive questions are included in interviews, or if study visits occur in the home setting.

Every effort will be made to ensure privacy and confidentiality to the participant. All surveys will be conducted virtually, or in-person at a safe distance and while following COVID-19 safety protocols or be self-report. If conducted over the phone or administered through the web, study staff will ask the participant to use headphones and/or find a private location in their home. If done through paper and pencil, the participant will be reminded to fill it out and place it in a sealed envelope to send back to the study team via packet pick up. If done in-person at school, study staff will allow the person to fill it out in private on a tablet or on paper but stay close by in case of questions.

VIII. Direct Personal and Social Benefits:

A. Describe any potential direct benefits the study offers to participants ("payment" for participation is not a direct personal benefit).

The study provides culturally adapted evidence-based interventions to those with elevated mental health distress. This will likely reduce distress for those enrolled.

B. Describe potential societal benefits likely to derive from the research, including value of knowledge learned.

This study will allow us to understand what impact brief and cultural adapted interventions have on AI/AN communities who are disproportionately affected by anxiety, depression, and suicidal thoughts and behaviors. Adapting a low cost, evidence-based practices such as safety planning and Caring Contacts may help with reduction of symptoms as well as providing those with known mental and behavioral health concerns with support in accessing appropriate services.

IX. Payment or Token of Appreciation:

A. Do you plan to provide a non-monetary token of appreciation (food, soap, tea, chlorine tablets, etc.) to study participants? If no payment is provided, the JHSPH IRB strongly encourages providing such tokens. If yes, please describe below.

There are no current plans to provide participants in this study with non-monetary tokens of appreciation.

B. If you plan to provide a monetary payment, describe the form, amount, and schedule of payment to participants. Reimbursement for travel or other expenses is not "payment," and if the study will reimburse, explain.

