All study staff will be managed and supervised by a local site team lead and/or site supervisor. This will involve regular debriefings with staff to review activities and identify any issues or challenges. In addition, consent and data collection forms and notes will be reviewed by the local site manager and study staff to ensure that study protocols are being properly adhered to. Any paper consent forms, data collection forms, and handwritten notes will be stored in a locked filing cabinet on site that will only be accessible by the local site managers. No data or forms will be accessed or allowed to be taken out of the room directly by anyone other than them. The site team lead/supervisor takes responsibility for collecting data records (forms and notes) from staff and ensuring that files are destroyed once the study is complete. The site team lead/supervisor will be in close communication with [name] to ensure these processes are adhered to. In the case of non-compliance, local site managers will inform [name] who will determine whether the non-compliance is serious and when to report it to the IRB.

C. Safety Monitoring:

1. Describe how participant safety will be monitored as the study progresses, by whom, and how often. Will there be a medical monitor on site? If yes, who will serve in that role and what is that person's specific charge?

The PI, [name], assumes responsibility for the safety of study participants. Study staff will be trained to monitor for the safety of study participants and report any concerns immediately to the site manager and the PI. Study staff will be trained in human subject's research and will be required to complete the CITI ethics module prior to any interaction with participants or study data. Certificates of human subject's completion will be kept on file at the Center for American Indian Health's office in Baltimore. A list of community resources will be provided with each assessment visit – either verbally by the study staff administering the survey or by paper.

At the end of any assessment administered, a notification will appear to the research program assistant if suicide risk (e.g., recent ideation and/or recent attempt) is indicated, the research program assistants will then respond in a graduated fashion based on the safety protocol outlined in 'Miscellaneous documents'.

- 2. If a Data Safety Monitoring Board (DSMB), or equivalent will be established, describe the following:

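### Dropped-off paper surveys fall outside the immediate suicide-item scoring that the supplied text promises, and the youth self-report SDQ cut-off differs between Table 2 and V.C.1.c

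*Combined protocol and SAP*

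**What the plan says.** **Suicide items.** VII.B.5 sets the standard: "Risk will be gauged by immediately scoring the suicide-related questions". It does this through REDCap flags on the CESDR-10 ideation item and automatic alerts to senior staff. X.C.1 adds: "At the end of any assessment administered, a notification will appear to the research program assistant if suicide risk" is indicated.

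**Paper.** Among the assessment modes, VII.D lists completion "by a self-administered paper packet dropped off by a study team member". VII.E tells participants who use paper to "place it in a sealed envelope to send back to the study team via packet pick up". For surveys done at school, VII.E instead has staff let the person "fill it out in private on a tablet or on paper but stay close by in case of questions".

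**When the alert fires.** V.C.1.iii says of paper forms that "data must be entered into REDCap as soon as the staff member has it back at the office". The on-screen notice to the interviewer follows that step: "Once entered into REDCap, for any participant who scores above pre-established cutoffs on mental health instruments or indicates suicide risk". The email works the same way: "An additional email alert to the site supervisor, PI and study coordinator will also occur when the data is uploaded to the server".

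**SDQ emotional subscale.** Table 2 in IV.A gives 5+ for caregiver report and 6+ for youth self-report. V.C.1.c describes the instrument under a heading that names both informants and gives one cut-off, 5+. V.B.1.c makes Table 2 the inclusion rule.

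**The concern.** Participants are selected for distress, and recent ideation is itself a route into the trial, so positive ideation answers are to be expected. The plan's safety response is built around REDCap: an answer is entered, it is flagged, and staff act. A sealed form waiting at someone's home has not entered that chain. If staff follow the visible text exactly, nobody is instructed to look at the ideation item until the form reaches the office and is keyed in. The participant may reasonably believe that the study team has been told.

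The SDQ discrepancy is a smaller matter of the same kind. The cut-off decides whether a youth is flagged and referred, and the document gives two values for youth self-report.

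**Working it through.** There is no stated figure to reproduce. The check sets the provisions side by side.

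**1. Time from completion to alert, by mode**

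- *Online, adults only.* The answer reaches REDCap when the data are uploaded and an alert follows. After working hours, VII.B.5 adds a text with crisis numbers and staff follow-up within 24 hours. Youth may not use this mode.
- *Tablet, or phone with staff reading the questions.* A staff member is involved and the notice appears once the data are in REDCap.
- *Paper at school.* Staff remain nearby. Office entry still precedes the alert, but the form is in staff reach straight away.
- *Paper left for pick-up.* Time to alert = wait for pick-up + transport to the office + opening and data entry. The supplied text asks for entry as soon as the form is back at the office. It sets no limit on the pick-up wait, the transport or the opening of the envelope. The total is above zero and has no stated maximum.

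**2. Do other provisions close the gap?**

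- *Scoring manual (V.C.1.iii).* It lets staff score paper by hand at baseline for symptom screening. Eligibility depends on that screening, so a baseline form has to be scored before the participant can proceed. No equivalent is described for 30 or 90 days. The gap is therefore mainly at those two assessments.
- *24-hour follow-up (VII.B.5).* It is written for adults who answer online after hours, and it starts from an alert. An unopened envelope produces none.
- *Staff available for questions on paper surveys (V.C.1.iii).* This does not say that staff read the ideation item.
- *Youth.* They are barred from the online mode, but nothing in the text limits dropped-off packets to adults.

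**3. SDQ cut-off for youth self-report**

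- The scale runs 0 to 10, which is 11 possible scores.
- Flagged under V.C.1.c: 5, 6, 7, 8, 9, 10. Flagged under Table 2: 6, 7, 8, 9, 10.
- The two sets differ by one score, 5, so 1 of 11 values is classified both ways.
- *Eligibility:* V.B.1.c points to Table 2, so 6+ applies and a self-report score of 5 does not qualify on this scale.
- *Alerts:* V.C.1.iii refers to pre-set cut-offs without listing them. The Table 2 footnote linking the values to the parent study's alerts is attached to the caregiver-report block.
- *Referral:* VII.B.4 names the SDQ for youth self-report but gives no number.
- *Youth concerned:* III.B estimates 264 × 10% = 26.4, about 26 eligible youth before refusals. Only those scoring exactly 5, and not flagged by another instrument, are affected.

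**The case against.** The strongest objection is that VII.B.5 is a summary. VII.A, VII.B.5 and X.C.1 all send the reader to a separate suicide-response document that was not supplied and may well set a paper turnaround. This stands as a limit. A reader might infer that the trial has no safe procedure for paper; the documents do not support that, because the governing procedure is unseen. What can be said is that the supplied text does not cover the case.

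It can also be argued that scoring immediately means on receipt, and that X.C.1 concerns assessments run by staff, whereas VII.D calls the packet self-administered. Both readings are possible. Neither supplies a pick-up or opening time, and X.C.1 speaks of any assessment, so the wording needs settling in either case.

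Other safeguards exist: paper is described as a back-up, a list of community resources accompanies each assessment visit, and everyone receives a coping plan and two early check-ins. These reduce frequency and general risk. They do not bring a written ideation answer to anyone's attention at 30 or 90 days.

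Opening the envelope on collection weakens the privacy that VII.E sets out to protect. That is a real trade-off, and the investigators and review boards should weigh it.

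On the SDQ, V.C.1.c is only an instrument description, its 5+ is right for caregiver report, and youth data are to be analysed descriptively. All true, which is why the point is a correction of wording.

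**Conclusion.** Both parts hold, at different weights.

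The paper gap should be fixed. In the supplied text, a dropped-off, sealed packet is not covered by the scoring and notification that VII.B.5 and X.C.1 promise, chiefly at 30 and 90 days. How many participants this touches cannot be estimated, because the share using paper is not given. The conclusion assumes that the separate procedures are silent on paper turnaround; if they are not, a citation and matching wording are enough.

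A reader might take the ±10-day assessment window as a 20-day allowance for leaving a packet out and compare it with the two weeks that the ideation item covers. The documents do not support this. The window governs when assessments are scheduled and the two weeks is a recall period; neither is a pick-up limit or a response standard. The finding is that no limit is stated.

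The SDQ conflict is real but small: one score, youth self-report only. A reader might infer that eligibility is ambiguous; it is not, because V.B.1.c makes Table 2 govern. What is unclear is which value drives alerts and referral.

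Neither part changes randomization, the adult power calculation or the planned analysis.

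**What to change.** **Paper packets.** If the Suicide Risk Safety Procedures already set a paper turnaround, cite it in VII.B.5. Otherwise state there that:

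- staff open the packet on collection, check the CESDR-10 ideation item (1+ is positive in Table 2) and start the safety response at that point;
- a short pick-up date is agreed at drop-off, for example the next working day, with the interval set by the investigators;
- participants are told at drop-off that staff will make this check;
- phone or in-person assessment, both already allowed, is used where a quick return trip is not practical;
- packets are not left unattended with youth; staff stay close by, as VII.E already provides at school.

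Reword VII.B.5 and X.C.1 so that, for paper, the promise is a check on collection. Even next-day pick-up is not immediate.

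**SDQ.** Amend V.C.1.c to 6+ for youth self-report and 5+ for caregiver report, and confirm that REDCap alerts and referrals use those values.

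**Cost.** For paper, a few minutes of staff time per packet and some pressure on travel to remote homes, which the phone option relieves. Privacy is slightly reduced, and some participants may answer less openly. For the SDQ, one wording change and one REDCap check.
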